8.2 ADVERSE EVENT RELATEDNESS

The relationship of the AE to the NeuroBlate[®] System Device (NBS) or the NeuroBlate[®] (LITT) procedure or surgical procedure will be determined by the Primary Investigator (PI) based upon the following definitions.

Definite: The AE follows a reasonable temporal and causative sequence from receipt (or attempted receipt) of the device treatment or procedure.

Possible: The AE follows a reasonable temporal sequence from receipt of the device treatment or procedure and the possibility of device treatment or procedure involvement cannot be excluded. However, other factors such as underlying disease, concomitant medications, or concurrent treatment are presumable.

Not Related: The AE has no temporal sequence from receipt of the device treatment or procedure, or it can be explained by other factors, including underlying disease, concomitant medication, or concurrent treatment. Note: If the event is determined to be "Not Related" to either the NBS or the Surgical Procedure, it is not considered a reportable AE.

8.3 SAFETY COMMITTEE

A Safety Committee will be used to review reported events to provide unbiased third-party adjudication for publications.

9 PROTOCOL DEVIATIONS

A deviation is defined as an event that did not occur according to the registry protocol. For the purpose of this registry, and in consideration of standard of care practices across study sites, anticipated protocol deviations include: improper consenting of subject (i.e. consent not obtained and improper consenting) and not completing study required questionnaires (if not completed at baseline only one deviation needs to be completed for that subject or if completed at baseline but a subsequent visit or questionnaire is not completed then a deviation for the missed timepoint needs to be completed) A deviation is not required if a questionnaire is not completed because the subject does not meet the age requirement for the validated QOL.

All deviations will be reported to Monteris Medical. It is the site's responsibility to report deviations in compliance with their Institutional Review Board.

10 DATA ANALYSIS

Data collected in this study is observational and there is no pre-defined study hypothesis. Descriptive statistics will be used to analyze data. Continuous variables will be summarized with means, standard deviations, minimums, and maximums. Categorical variables will be summarized in frequency distributions.

11 CORE LAB

MRIs will be collected according to the Study Visit Schedule. Standard of Care MRI imaging will be sent to the Imaging Core Lab for analysis as per the sponsor. The immediate pre-operative and immediate post operative images (to include T1 pre-contrast, T1 post-contrast, T2 FLAIR, and any other sequences obtained during these timepoints as per standard of care at that institution) are required for upload to Monteris. Per core lab or cohort specific needs, additional standard of care imaging at various timepoints may be requested by the sponsor in accordance with the site clinical trial agreement (CTA). The sponsor will not request MRI sequences or imaging at timepoints that are not considered standard of care per the institution. Please refer to the Image Acquisition Protocol for additional information.

12 STUDY MANAGEMENT

The study will be performed in accordance with all requirements set forth in the U.S. regulations, 21 Code of Federal Regulations (CFR) Parts 50 (Protection of Human Patients), 56 (Institutional Review Board), and applicable requirements from the reviewing IRB for the study at each site.

12.1 DATA COLLECTION AND MANAGEMENT

The study data will be hosted in an electric data capture (EDC) system. The EDC system will be compliant with the U.S. regulations, 21 CFR part 11, Electronic Records; Electronic Signatures.

All required data for this study will be collected on standardized Case Report Forms (CRFs).

Qualified study staff at each investigational site will perform primary data collection drawn from source document (e.g. hospital chart) review. All CRFs will be subject to review for omitted data, gross data inconsistencies, illegible data, and deviations. Any deficiencies or deviations will be reviewed, and any necessary action determined (e.g. data query, communication to the study center).

Data review (including crosschecks) will be performed and any discovered errors will be reported to the study site using the data correction and query process (as necessary). The study site will review the query, respond, and make any necessary corrections or comments. The data cleaning cycle will be repeated until all data are considered clean.

13 ADMINISTRATIVE RESPONSIBILITIES

13.1 SPONSOR RESPONSIBILITIES

The Sponsor's responsibilities for this study are to:

- Select qualified clinical investigators and study sites
- Provide study protocol training to participating study sites including the Investigator and staff conducting the study
- Provide financial support to each study site which is fair, reasonable, and equitable to fair market value
- Follow/promote all applicable regulatory standards per CFRs at each study site
- Own and control the use of the data, including review and approval of study-related publications/presentations, etc.

13.2 INVESTIGATOR RESPONSIBILITIES

The Primary Investigator for each site is responsible for ensuring the study is conducted according to:

- All signed agreements (including financial disclosures)
- The Study Protocol
- IRB guidelines
- Applicable FDA regulations

The Investigator for each site may not begin enrollment until Sponsor receives and approves (when necessary) required documents, including a completed and signed Investigator Agreement/Clinical Trial Agreement (or equivalent), Protocol Signature Page, IRB and ICF approvals.

It is acceptable for the Investigator to delegate one or more of the above functions to an associate or Sub-Investigator or trained Study Coordinator; however, the Investigator remains responsible for the proper conduct of the clinical investigation, including obtaining and documenting proper study informed consent, collecting all required data, submitting accurate and complete CRFs, etc.

At each site, appropriate procedures must be followed to maintain subject confidentiality according to appropriate local regulations (e.g. Health Insurance Portability and Accountability Act in the U.S.). Each site may have its own internal procedures or requirements for use and release of subject medical

information in research studies. Each Investigator is responsible for obtaining appropriate approvals, consents, or releases of medical information as dictated by their relevant patient privacy laws.

The study is not transferable to other sites attended by the Investigator unless prior approval is obtained from the appropriate IRB and the Sponsor.

13.3 INSTITUTIONAL REVIEW BOARD (IRB) APPROVAL

Investigators must submit the study protocol and ICF to their reviewing IRB and obtain IRB written approval before being allowed to conduct and participate in the study. Each Investigator must submit to the Sponsor a copy of the IRB approval letter, specific to this protocol and addressed to Investigator, certifying study approval prior to enrolling subjects into the study. This approval letter should identify the study name, study protocol number (including revision number), the date of the approval as well as the expiration date of such an approval. The Investigator is also responsible for fulfilling any conditions of approval imposed by the IRB, and for maintaining continuation of the approval during the entire study period. The Investigator must provide the Sponsor with copies of such approvals.

13.4 CONFIDENTIALITY

All information and data sent to the Sponsor concerning subjects or their participation in this study will be considered confidential. All data used in the analysis and reporting of this evaluation will be used in a manner without identifiable reference to the subject.

13.5 DEVICE ACCOUNTABILITY

Device accountability will NOT be required as there are no investigational devices used in this study.

14 MONITORING

The Sponsor or a Sponsor representative will monitor the progress of the study as described in the Study Monitoring Plan. The Investigator consents to visits by the staff of the Sponsor or its representatives to review the study subject medical records, including any test or laboratory data that might have been recorded on diagnostic test media (e.g. MRI).

Subject Records

The Sponsor will request that any source documents to be submitted to the sponsor, sponsor representative be de-identified (subject's name and other personal identifiers must be removed and replaced with the study subject ID).

These source documents may include but not be limited to:

- Admission, procedural, and discharge reports/notes
- Completed questionnaires
- Documented pain/KPS scores
- Any documentation relevant to a protocol reportable AE/SAE
- Imaging

15 INVESTIGATOR REPORTS AND RECORDS REQUIREMENTS

The Investigator is responsible for the completion and submission to the Sponsor of all CRFs, AEs or other reportable study events (e.g. procedure related complications), and deviations from the protocol. If any action is taken by an IRB with respect to the study, the information must be forwarded to the Sponsor in a timely manner.

The Investigator shall prepare and submit complete, accurate, and in a timely manner, the reports listed in Table 2 below. In addition to this list, individual IRBs may add additional requirements and/or require a different notification time frame.

. -

-

Type of Report	Notification prepared by Investigator for	Notification Time Frame		
Reportable Serious Adverse Events as Described in Section 8	Sponsor	As soon as possible, preferably		
Death or Serious Adverse Event	IRB per policy	within 48 hours after discovery of event.		
Withdrawal of IRB Approval	Sponsor	Within five (5) working days.		
Deviations to the Protocol	Sponsor IRB per policy	As soon as possible after occurrence of deviation.		

All data must be stored and retained by the investigative site for a minimum of 2 years following a notification from Sponsor that all investigative sites are complete, terminated, or discontinued. Should the investigator withdraw from the responsibility of retaining study records, then custody of the records transfers to a person assuming responsibility. Sponsor will be notified in writing of new custodian by the investigative site.

16 USE OF INFORMATION AND PUBLICATION

The LAANTERN Registry will follow the Publication Plan (CL10084) which outlines the guidelines and expectations for LAANTERN publications. For primary manuscript(s) generated from this study, the National Principal Investigator of the study may be granted first and/or senior authorship. The order of subsequent authors will be determined by their contribution. The number of maximum names on the publication will depend on the maximum number of authors allowed by the publisher.

Manuscript ideas may be generated by any Investigator in the study. Investigators should submit publication ideas to the Sponsor for review. An Investigator may also want to publish the study experience from his/her own site. The Sponsor reserves the right to review and approve all publications and presentations utilizing the study data. The Investigator may proceed with the publication when notified by the Sponsor.

For publication purposes, this study will be submitted for inclusion in the clinical trial study at: https://clinicaltrials.gov/ct2/show/NCT02392078

Statistical Plan
June 2020

NCT02392078

LAANTERN Statistical Methods

General Summary

Descriptive statistics will be used to summarize the patient population data, operative data, and follow-up data. For continuous variables, the total count, mean, standard deviation, minimum, and maximum will be provided. For categorical variables, the total count and percentage will be provided.

Survival Analysis with Censoring/Truncation

The survival analysis will be used to estimate time-to-event probability and will take into account right-censoring or left truncation. Left truncation occurs when patients are enrolled into the study after the NBS Index Procedure occurs. The survival function will be estimated using the Kaplan-Meier method. The hazard rate over time may be provided along with corresponding 95% confidence limits to assess potential time-dependent trends.

Comparative Analysis

Comparisons in survival/event rates may be made between subgroup of patients with various disease states (for example, epilepsy vs tumor, etc.), differences in baseline demographics, product models (for example, new device iterations, etc.), or other factors that are deemed important for understanding patient outcomes or risk.

Proportional Hazards Regression

The proportional hazards regression models may be used for time-to-event analysis. Predictors may include patient baseline variables in addition to the risk factor of interest.

Determination of Patients for Analysis

All enrolled patients who had procedures with the NBS will be included in this analysis. Additional analyses may be performed for subgroups of interest based on all enrolled patients with valid data.

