Karnofsky Performance Scale (KPS)	 The KPS will be collected for brain malignancy subjects only, and for subjects 16 years and older. The scale runs from 100 to 0, where 100 is "perfect" health and 0 is death: 100 - Normal; no complaints; no evidence of disease. 90 - Able to carry on normal activity; minor signs or symptoms of disease. 80 - Normal activity with effort; some signs or symptoms of disease. 70 - Cares for self; unable to carry on normal activity or to do active work. 60 - Requires occasional assistance but is able to care for most of his personal needs. 50 - Requires considerable assistance and frequent medical care. 40 - Disabled; requires special care and assistance. 30 - Severely disabled; hospital admission is indicated although death not imminent. 20 - Very sick; hospital admission necessary; active supportive treatment necessary. 10 - Moribund; fatal processes progressing rapidly. 0 - Dead
Lansky Performance Scale (LPS)	The LPS will be collected for brain malignancy subjects only, and for subjects between 1 year and 16 years of age. The scale runs from 100 to 0, where 100 is "perfect" health and 0 is death: 100 – Fully active, normal 90 – Minor restrictions in strenuous physical activity 80 – Active, but gets tired more quickly 70 – Greater restriction of play and less time spent in play activity 60 – up and around, but active play minimal; keeps busy by being involved in quieter activities 50 – Lying around much of the day, but gets dressed; no active playing participates in all quiet play and activities 40 – Mainly in bed; participates in quiet activities 30 – Bedbound; needing assistance even for quiet play 20 – Sleeping often; play entirely limited to very passive activities 10 – Doesn't play; does not get out of bed 0 – Unresponsive
Serious Adverse Event (SAE)	 Adverse Event that: (a) Led to death (b) Led to serious deterioration in the health of the subject, that either resulted in life-threatening illness or injury A permanent impairment of a body structure or a body function In-patient or prolongation of existing hospitalization Medical or surgical intervention to prevent permanent impairment to a body structure or a body function (c) Led to fetal distress, fetal death or a congenital abnormality or birth defect

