7.2 REGISTRY REQUIRED QUESTIONNAIRES

Completion of questionnaires is required for this study. Questionnaires may be completed remotely via phone, mail or email if an office visit will not be completed. If a given questionnaire is not completed for a subject at Baseline, analysis of questionnaire data for this subject is not possible. Therefore, if the Baseline Questionnaire is not completed, this questionnaire is not required during follow-up and will not be compensated.

EuroQoI-5D (EQ-5D) (All Subjects 16 years old and older); EuroQoI-5D-Y (EQ-5D-Y) (All subjects 8-15 years old)

The EQ-5D provides simple, generic measure of health for clinical and economic appraisal. This questionnaire consists of 2 pages: 1) the EQ-5D-3L descriptive system and 2) the EQ Visual Analogue scale (EQ VAS). The descriptive system assesses subject's mobility, self-care, usual activities, pain/discomfort, and anxiety/depression. The EQ VAS records the respondent's self-rated health on an approximately 20 cm vertical, visual analogue scale with endpoints labelled 'the best health you can imagine' and 'the worst health you can imagine'. The VAS will be utilized to assess subject pain at the lesion site or on head.

FACT–Br (CNS malignancy subjects only 18 years old and older) **FACT-Peds-Br-Adolescent** (12-17 years old) and **FACT-Peds-Br-Child** (7-12 years old)

Functional Assessment of Cancer Therapy-Brain (FACT-Br) is a commonly used instrument measuring general quality of life that reflects symptoms or problems associated with brain malignancies across 5 scales. FACT-Br is a brain tumor specific 50-item questionnaire for subjects who are not neurologically incapacitated. It will provide an overall QOL score as well as sub-scores for physical well-being, social/family well-being, emotional well-being, functional well-being and concerns relevant to subjects with brain tumors.

QOLIE-31 (Epilepsy subjects only >18 years old): **QOLIE-AD-48** (11-18 years old) **QOLCE-55** (Care Giver provider).

The Quality of Life in Epilepsy Inventory (QOLIE-31) contains seven multi-item scales that tap the following health concepts: emotional well-being, social functioning, energy/fatigue, cognitive functioning, seizure worry, medication effects, and overall quality of life. A QOLIE-31 overall score is obtained using a weighted average of the multi-item scale scores. The QOLIE-31 also includes a single item that assesses overall health.

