7.5 STUDY COMPLETION OR WITHDRAWAL

Subjects will complete the study once their 5-year follow-up visit is completed or if the subject was prematurely withdrawn prior to their 5-year visit.

The subject may be prematurely withdrawn from the study for the following reasons:

- Subject did not have NeuroBlate[®] Procedure.
- Subject Lost to Follow-up: All efforts shall be made to document at least 3 attempts to contact subject, which would include a certified letter to the subject. If attempts to contact the subject fail, the subject may be withdrawn from the study and considered lost to follow up.
- Subject Withdrawal: A subject may voluntarily withdraw from the study at any time.
- Investigator Withdrawal of Subject: An Investigator may withdraw a subject for reasons which may include noncompliance, failure to keep appointments, etc.
- Subject Death: If subject passed away, the expiration date will be considered the end of study date. All feasible attempts should be made to confirm date of death, as this is key for overall survival analysis.

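### KPS and quality-of-life means among observed malignancy subjects can rise, or understate decline, through attrition alone; no change from baseline or rule for death is specified

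*SAP*

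**What the plan says.** The General Summary of the SAP covers population, operative and follow-up data with one rule: "For continuous variables, the total count, mean, standard deviation, minimum, and maximum will be provided". Protocol section 10 agrees: "Continuous variables will be summarized with means, standard deviations, minimums, and maximums". Categorical variables get counts and percentages. The SAP addresses censoring only for time-to-event outcomes. Its analysis set is broad ("All enrolled patients who had procedures with the NBS will be included in this analysis"), and it adds: "Additional analyses may be performed for subgroups of interest based on all enrolled patients with valid data". Neither statement says what happens to a subject with no score at a visit.

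Four protocol provisions decide who has a score:

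- Section 7.5, on death: "If subject passed away, the expiration date will be considered the end of study date".
- Section 1, on who has a KPS: "The KPS will be collected for brain malignancy subjects only, and for subjects 16 years and older". LPS is the counterpart for younger malignancy subjects. The bottom of the KPS reads "10 - Moribund; fatal processes progressing rapidly. 0 - Dead".
- Section 7.1: KPS and LPS are recorded as done in routine care, so a living subject may have none.
- Section 7.2: "FACT-Br is a brain tumor specific 50-item questionnaire for subjects who are not neurologically incapacitated". The same section says that a subject without a baseline questionnaire cannot be analysed for that questionnaire.

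Table 1 schedules these measures at baseline, 1, 3, 6 and 12 months and then yearly to 5 years (KPS/LPS also at discharge). Section 5.1 lists cognitive and quality-of-life outcomes as Objective 4.

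**The concern.** A reader of a table of means by visit will compare columns and take the difference as patient change. That is valid only if the same kind of subject contributes to each column. In brain malignancy this is doubtful: subjects with poor function may die sooner, and those alive but incapacitated fall outside the group FACT-Br is meant for. Each later column could then average a better-functioning remainder, and the difference between columns would mix change within patients with selective loss.

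No hypothesis test is at stake, since the registry is descriptive. What is at stake is the published description of function and quality of life after treatment. Protocol section 3 says the objectives are designed with publication in mind.

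**Working it through.** **No planned figure to reproduce.** The documents give no KPS distribution, survival figure or expected change. Every number below is an assumption or follows from one.

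**Step 1. Exact two-group case.** Let a share f start at low score L and the rest at high score H, with sL and sH the shares still observed at the visit.

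Observed mean = [f·sL·L + (1−f)·sH·H] / [f·sL + (1−f)·sH]

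Take f = 0.5, L = 60, H = 90, so the baseline mean is 75.

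- Nobody changes, 30% and 70% observed: (0.15×60 + 0.35×90)/0.50 = 40.5/0.50 = 81.0, a rise of 6.
- Nobody changes, 40% and 60% observed: (0.20×60 + 0.30×90)/0.50 = 39/0.50 = 78.0, a rise of 3.
- Nobody changes, 50% and 50% observed: 75.0, no rise.
- Everyone loses 5 points, 30% and 70% observed: (0.15×55 + 0.35×85)/0.50 = 38/0.50 = 76.0, an apparent gain of 1.
- Everyone loses 5 points, 40% and 60% observed: 73.0, an apparent loss of 2.

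So the effect needs loss that depends on the score. Unrelated loss produces none.

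**Step 2. Simulation for malignancy KPS.** Assumptions: 400,000 subjects; KPS normal with mean 80 and SD 12, limited to 30-100 (achieved mean 79.7); exponential survival with median 12 months; log-hazard slope of −0.02 to −0.04 per KPS point; a score for every survivor.

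| Scenario | 12 months | 24 months |
|---|---|---|
| Nobody changes, slope 0 | no rise | no rise |
| Nobody changes, slope −0.02 to −0.04 | mean 81.6 to 83.2 (up about 2 to 3.5) | mean 83.2 to 85.8 (up about 3.5 to 6) |
| Everyone loses 0.5 points per month, same slopes | true loss 6, shown as 4.2 to 2.5 | true loss 12, shown as about 8.5 to 6 |

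At 3 months the rise with nobody changing is about 1 point or less.

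**Step 3. Different inputs.** With baseline mean 74.7, SD about 15, median survival about 12 months and every patient losing 3 points per year, the 12-month mean is 71.7, 73.6, 75.7 and 78.1 for hazard ratios of 1.0, 1.2, 1.5 and 2.0 per SD lower KPS. A declining cohort therefore appears to improve at 1.5 and above, but not at 1.0 or 1.2.

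**Step 4. Paired change.** In the Step 3 population, the mean change from own baseline among those observed is 0.0 when nobody changes and −3.0 at 12 months when everyone loses 3 points per year, at every hazard ratio. It cannot be positive if no patient improves. It still describes only the subjects observed.

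**Step 5. Pooling diseases.** EQ-5D is collected across diseases. Suppose 20% have epilepsy (score 75, 95% observed) and 80% a tumour (score 60, 35% observed). The baseline mean is 0.2×75 + 0.8×60 = 63.0. At follow-up it is (0.19×75 + 0.28×60)/(0.19 + 0.28) = 31.05/0.47 = 66.1, with nobody changing. Hence the need to report by disease group.

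**The case against.** The strongest reply is that the plan never commits to this analysis. The SAP names neither KPS nor any questionnaire and does not mention summaries by visit. Use of available scores is inferred from its silence together with the end of follow-up at death. This stands: a reader might infer that the plan excludes deaths from the KPS summary despite the scale's zero for death, but the documents neither exclude deaths nor score them as 0. The gap is the missing rule.

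Other points on that side:

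- *Baseline comparison is foreshadowed.* The baseline requirement in section 7.2 makes most sense if change from own baseline is intended. That is fair for questionnaires, but no such analysis is defined and the requirement does not cover KPS or LPS.
- *Attrition is visible.* The SAP gives the count with each mean and plans Kaplan-Meier estimates. This lowers the risk of misreading. It does not separate the dead from the unable and the missing, and it does not correct the mean.
- *KPS moves in 10-point steps and could be tabulated as categories.* True, but percentages among those observed carry the same selection. With nobody changing, the share of survivors at KPS 70 or more goes from 80% to 88-94% at 24 months in the Step 2 simulation.
- *A mean among survivors is a legitimate description.* It is, if labelled as such and not read as change.

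**Conclusion.** The concern holds as a gap with a predictable direction of error. The only summary stated for continuous follow-up data can mislead when compared across visits, because nothing is specified for change from baseline, death or missing scores. Under the Step 2 assumptions the distortion in malignancy KPS is about 2 to 3.5 points at 12 months and 3.5 to 6 at 24 months. It disappears if loss is unrelated to score.

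Two stronger readings are not supported. First, one might infer that the tables would show stable or improving function in a declining cohort. They can, but in the Step 2 declining scenario the mean still falls, only by too little; an apparent rise needs a slower decline or stronger selection, as in Step 3. Second, one might infer that Objective 4 as a whole is answered wrongly. The size was worked out only for malignancy KPS, which is a performance measure. For FACT-Br and EQ-5D the mechanism is plausible but unquantified, and the argument from death does not extend to epilepsy subjects on QOLIE-31.

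**What to change.** Add to the SAP, for KPS/LPS, FACT-Br and EQ-5D, by disease group and visit:

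1. The paired change from the subject's own baseline among those with both values, with a statement that it describes only subjects observed.
2. The number of treated subjects due at the visit, split into observed, dead, alive but unable to answer, and missing.
3. A statement that differences between unpaired visit means are not interpreted as change.

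Optionally, for malignancy KPS, report the percentage of treated subjects due who are alive with KPS at or above a threshold fixed in advance. The value 70 would serve as an example; it is not in the documents. Deaths count as 0, as the scale defines. Living subjects with no KPS are shown separately, with bounds that count them all as above and then all as below the threshold.

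The cost is a few more table rows and somewhat less favourable results. Scores and dates of death are already collected. Separating unable from missing needs a recorded reason for non-completion, which the documents do not mention; without it, those two groups should be reported together.
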